We will recruit 900 participants. We will no longer be limiting our participants to these study sites and have expanded to include study participants from across the US. Using active and passive recruitment methods, the on-site project coordinator at each site will oversee and participate in recruitment efforts. The study staff hired through this project, on-site coordinator and the peer-to-peer networking efforts at each site will be used to recruit study participants. Each of our sites have previously participated in recruitment efforts for projects similar to the one proposed here and will be able to successfully recruit the study sample for this project. Our study participants will all have face-to-face contact with our study staff as a means to verify participants' identity. In order to accomplish this using an online sample, we will verify participants' identity using video conferencing (i.e. Zoom). Note: As per the RFA, we will ensure that we have an adequate number of participants in each age group (e.g., 13 year olds) to conduct valid sub-group analyses. Based on our power analysis, we will recruit at least 70 participants in each age.

C.3. Procedures for Maximizing Research Integrity.

To Maintain Blind Assessment, we will collect data through electronic surveys on tablet computers. Interviewers will remain in the room to ensure comprehension. Electronic survey completion offers several advantages: (1) It yields more accurate responses than face-to-face interviews about sensitive topics. (2) Participant can complete measures at their own pace. (3) Questions are answered privately increasing anonymity. (4) The interview structure permits skipping follow-up questions when the stem is answered negatively. (5) Computer delivery ensures uniform administration. Procedures for Maximizing Retention. We will use multiple strategies to reduce attrition.^{79,80} At baseline and follow up interviews, we will update contact information and encourage ongoing communication. We will offer multiple reminders via text, email or calls, based on participants' preference. To ensure follow-up assessments can be conducted for those who move, we will provide access to the assessment via link into a secure server, where data is encrypted at entry and no identifiers are collected.

C.4. Description of study population.

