We plan to enroll 900 13-18 year old male youth across the U.S.. We will recruit potential participants using both online social networking and sexual networking websites (e.g., Facebook, Grindr, BlackGayChat, Scruff, and new sites identified by pilot participants in Aim 2). Social networking and sexual networking sites are accessible to individuals across the US and do not require individuals to live in a particular city to access the information within. We will recruit through these networks using an open platform which will allow us to reach potential participants from all 50 states and not limit us to a particular city/state. Utilizing these open access platforms will allow us to expand the range of participants we can reach. Potential participants who click on an online survey banner advertisement will automatically be linked to the study landing page on REDCap that contains a consent form. Potential participants will be required to read the informed consent document before indicating whether or not they consent; this will be encouraged by requiring participants to scroll through the entire consent before they can choose to consent to the study. During the informed consent process, the minimal risks, the anonymous and voluntary nature of participation, and the fact that participants can stop their participation at any time are described. Clicking the consent button will indicate that the participant has read the consent form and agrees to participate. A button to allow participants to print the consent form for their records will be located at the end of the consent form document. We will provide our email and phone number contacts on the consent form in case participants have further questions about the study. Potential participants can exit the website at any time by closing their browser. Consent or lack thereof will be documented in the electronic database by the stored variable indicating consent or lack of consent.

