Although Federal regulation requires that researchers obtain written informed consent for research on human subjects, under 45 CFR 46.117(c) written consent can be waived for research that involves minimal risk to participants and involves no procedures for which written consent is normally required outside of the research context. This research meets that criterion. We propose an alternative approach where participants click a button, signifying that they have read the informed consent page and agree to participate in the study. An advantage of internet-based studies is that the consent form is available for the subject to review and/or print at any time. This strategy complies with the requirement of 46.117(c) that participants are given a written statement describing the research and

risks. We have used these procedures without a known adverse event in 6 previous Internet studies, enrolling thousands of participants online.

Once online consent is provided, potential participants will complete a brief online screener survey (provided in English) to determine study eligibility. Potential participants will have the option to complete the online survey on their computer, Smartphone, or tablet. If ineligible, the individual will be automatically routed to a webpage that thanks them for their time and states that they are not eligible at this time. The webpage will contain links to national and local prevention resources, such as HIVtest.org, CDC.gov, and <http://www.teenhealthandwellness.com/static/hotlines>.

C.8.1. Eligibility screening.

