Potential participants will either call, text or email the project via the project phone number or email address; or, if contact information is gathered at the recruitment venue, be called, texted or emailed by project staff. Screening will be conducted over the phone, online, or in person for walk-ins; screening will **not** be conducted by email. Each potential participant will be screened for eligibility using the full screening instrument. If a parent is present at the time of potential study recruitment or enrollment, such activities would only take place in a private location away from their parents. At the same time, the risk of negative parental involvement is mitigated if a parent is at the health visit with their child at a community health center such as Callen Lorde Community Health Center, as they are healthcare and related services providers targeted to lesbian, gay, bisexual, and transgender communities. If a parent is accompanying a child to a visit at a community health center with this focus, it is likely that the parents are already aware of their child's sexual health practices.

The following verbal script is a guide to describe the screening process and privacy issues, as outlined in Appendix C: "Hi. I work with [e.g. Callen-Lorde Community Health Center] on a research study called MyPEEPS Mobile. Have I reached <insert name>? The study will involve (number of appointments questions. It will only take a minute or two. Some of the questions are personal. Your involvement is voluntary, your responses will be kept private, and you can refuse to answer a question or stop at any time. Information we gather from you will not identify you individually. Are you interested?" The full screening will only take a few minutes (Appendix C). If a potential participant is screened and found eligible and willing to participate then he will voluntarily provide written informed consent. Contact information will be destroyed if youth decline study participation; however, a count of eligibles and declines (active and passive) will be maintained. Secured information about those who participated in the pilot phase will be referenced during trial enrollment in order to verify that they indeed did not participate in the pilot. If it is determined during trial enrollment that a young person participated in the pilot, they will be deemed ineligible to be in the trial and cordially told so.

C.8.1.a. Secondary Screening to Confirm Eligibility

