Participant eligibility will be confirmed in person prior to obtaining informed assent/consent. For participants who are enrolled online, we will also use a form of video conferencing (eg. Zoom, etc) so that participants can show an ID and verify their identity.

C.8.2. Informed assent/consent.

Upon arrival at the enrollment visit we will collect written informed consent (18 year olds) (assent for 13-17 year olds) for enrolling men into the study trial (See Protection of Human Subjects and Inclusion of Children). The informed consent form provides details of the study procedures, risks, benefits, site contact information, and the nature of confidentiality and voluntary participation. The consent process also covers information on the trial and compensation for time. A baseline visit will be conducted involving a behavioral assessment (see questionnaires in Appendix A). The baseline assessment is expected to last approximately 1.5-2 hours and participants will be given \$25 as a token of appreciation for their time. YMSM will then be randomized to the intervention or delayed intervention

arm.

C.8.3. Randomization to intervention and delayed intervention study arms.

Using the randomization approach described below, there will be random or minimally biased assignment of subjects to study arms. We will use block randomization for this study,⁸² stratified by site and each category of study participants with have randomly permuted blocks to reduce opportunities for selection bias we will use a variable permuted randomization block design where the block size itself is randomly selected (i.e., blocks of four to eight). The advantage of the permuted block design is that treatment assignment is predetermined before the trial begins and then assignment remains static throughout the course of the trial.⁸³ Blinding and random assignment will be maintained through continuous supervision by key members of the research team. All staff, and participants will be kept blinded to outcome measurements during data collection.⁸⁴ This technique will maintain complete randomness of the assignment of a subject to a particular group. Participants will be randomized based on the use of computer-generated random numbers at baseline.

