Follow-up visits will be scheduled within a target window of 2 weeks before to 2 weeks after based on participant availability and site capacity; visits may be scheduled approximately one week before or up to about four weeks after the target follow-up date. Timing of follow-up visits is scheduled to allow site flexibility while still scheduling follow-up visits within a reasonable time span. If an individual misses one of the follow-up visits (e.g., 6 month visit for intervention group), then we will still attempt to collect their 9 month visit data. Every effort will be made by staff to ensure that participants are assessed in follow-up visits within, first, the target window, and second, the acceptable window. After consultation with the Co-I, the PI will decide how best to handle the situation for the individual participant and point in time that he contacted. For example, if a

participant was out of the country during the 3-month window and eventually calls the site at the 5-month point, the on-site study coordinator will consult with Drs. [name] or [name].

We will also review participant's medical records, if available, for care relating to sexual health such as HIV/STI testing and results, PrEP use, and risk factors starting from study enrollment onward.

C.10. Design Considerations.

The study team thought carefully about our design considerations regarding the collection of biological specimens for either HIV or other related STIs, but decided against it for two reasons: (1) from our experience in the field, we believe the incidence and prevalence rates of both HIV and STIs will be relatively low in this young age group, making testing not particularly helpful for either main or secondary outcomes, and (2) in certain geographic regions, such as the South, that adding a specimen collection might make it more difficult to obtain a waiver of parental consent for participation in this research, which we believe is of paramount importance. In addition, given that HIV/STI testing will be addressed in MyPEEPS Mobile intervention, and is an outcome of interest, we will not provide HIV/STI testing for study participants. Instead all study participants will be provided access to HIV/STI testing resources at the study endpoint. Importantly, participants are expected to continue normal healthcare activities during the course of the study and will be offered HIV/STI testing referral information.

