In addition to HIV/STI testing referral information, if during the course of participation, study staff identifies any young person who screens for moderate/high levels of substance use or mental health problems, they will be referred to local providers of care as well as to the TREVOR hotline if appropriate. Study staff will use screening instruments that are used commonly in adolescent primary care. If a young person reports abuse either sexual or otherwise, we will screen for imminent risk and make a report of the abuse according to state-specific rules. We will do a "well-being" de-briefing with all participants at the end of each visit. If they report being upset, we will screen for imminent risk of suicidality. We will not ask specifically about criminal behavior, e.g., stealing, vandalism, etc.

Table 3. Outcome Measures

	Pilot Study		Multi-Site RCT – Timepoints (months)				
	Pre-Test	Post-Test	Baseline	3	6	9	12
Demographics							
Sociodemographic: (e.g., age, race/ethnicity level of education, housing status)	▪		▪				
Technology Assessment	▪		▪				
Functional Health Literacy ⁸⁸	▪		▪				
Information Privacy Concerns ⁸⁹	▪		▪				
Primary Outcome Measures							
Sexual risk behaviors (adapted from AIDS-Risk Behavior Assessment) ⁹⁰⁻⁹²	▪	▪	▪	▪	▪	▪	▪
nPEP and PrEP Use (if guidelines change for under 18 years)	▪	▪	▪	▪	▪	▪	▪
HIV and STI Testing	▪	▪	▪	▪	▪	▪	▪
Intermediate Outcome Measures							
Self-efficacy for safer sex and situational temptation for unsafe sex ⁹³	▪	▪	▪	▪	▪	▪	▪
Condom Errors ⁹⁴	▪	▪	▪	▪	▪	▪	▪
Secondary Outcomes – Behavioral Intention							
Intent to have anal sex	▪	▪	▪	▪	▪	▪	▪
Intent to use condoms during anal sex	▪	▪	▪	▪	▪	▪	▪
Intent to uptake PrEP/nPEP (if guidelines change for	▪	▪	▪	▪	▪	▪	▪

under 18 years)						
Program Evaluation (* = intervention; ✓ = delayed intervention)						
Knowledge of and beliefs about the content of the MyPEEPS Mobile	▪		*			✓
MyPEEPS Intervention Acceptability and Tolerability ⁹⁵	▪		*			✓
Information System Success ⁹⁶	▪		*			✓

C.11. Study Outcomes.

Our outcome measures have been used in our MyPEEPS pilot study with YMSM (R34MH079707; PI: [name]). **We have 4 levels of outcomes:** primary, secondary, intermediate and program evaluation. A detailed list of outcome measures within each category and the time points when they will be collected is listed in Table 3. We also detail the primary and intermediate outcome measures below.

C.11.a. Primary Outcome Measures.

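### Online consent calls participation anonymous, although neither screening nor trial participation is; the exposure lies mainly at the screening stage and a wording change removes it

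*Combined protocol and SAP*

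**What the plan says.** **What youth are told.** C.8 (Online Study Procedures) describes a landing page, reached from a banner advertisement, that carries a consent form. During that process "the anonymous and voluntary nature of participation, and the fact that participants can stop their participation at any time are described". C.8 proposes that the participant then clicks a button, "signifying that they have read the informed consent page and agree to participate in the study". The next step is the screener: "Once online consent is provided, potential participants will complete a brief online screener survey". The verbal guide in C.8.1 (Eligibility screening) tells the potential participant: "Information we gather from you will not identify you individually". Section C.3, on remote follow-up for people who move, describes a secure link "where data is encrypted at entry and no identifiers are collected".

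**What the trial does.** C.8.1.a uses video conferencing for online enrolees "so that participants can show an ID and verify their identity"; C.1 and C.2 also provide for identity checks by video. C.13 has locator details updated at 3, 6, 9 and 12 months, with contact continuing until the participant asks to leave. C.9 states: "We will also review participant's medical records, if available, for care relating to sexual health such as HIV/STI testing and results". Under C.10, if a young person discloses abuse, staff will "make a report of the abuse according to state-specific rules".

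**What comes later.** C.8.2 describes a consent form (assent at ages 13-17) at the enrolment visit that covers confidentiality. C.1 sends remote participants the e-consent link only after their identity has been verified.

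**The concern.** Anonymous and confidential are different undertakings. Anonymous means that nobody can connect the answers to a person. Confidential means that the study can make the connection, protects it, and may have to break it in stated circumstances. The plan describes the first and operates the second.

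The people addressed are 13 to 18 years old. Under the eligibility criteria in A.3, screening has to establish attraction to or sexual activity with males, and self-reported HIV status. A young person who answers in the belief that no one can trace the reply has been given an inaccurate basis for deciding whether to answer. C.8 also relies on the click page as the written statement that supports waiving written consent, so its accuracy carries weight. Because the trial outcomes are self-reported, perceived privacy could in principle affect reporting as well, but the documents give nothing from which to size such an effect.

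**Working it through.** No arithmetic beyond an age count applies. The check is whether any stage of the study fits the word *anonymous*.

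1. **Scope of the word.** C.8 applies it to participation in general and treats the click as agreement to join the study. No section restricts it to the screener or withdraws it. The order of events (click, then screener) does suggest that screening may have been the intended scope, so both stages need testing.

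2. **Screening stage.** B.2.8 draws focus-group participants from youth who screened for the trial and were ineligible because they reported female sex assigned at birth. Selecting and approaching them requires that a screener answer be connected to a contactable person. B.2.8 does not say how they are reached. An invitation on the ineligibility page would avoid the connection, but C.8 describes that page as a thank-you with links to resources and mentions no invitation. C.8.1 provides for destroying contact details when a youth declines and makes no such provision for those found ineligible. The C.8.1 script opens by asking for the person by name, shortly before assuring them that the information will not identify them. Screening as planned is therefore not anonymous.

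3. **Enrolled stage.** ID is shown on video (C.1, C.2, C.8.1.a). Online enrolees are emailed the baseline survey, and those in the intervention arm who have not logged in within 24 hours are telephoned (C.8.3). Locator details are held and updated (C.13), medical records are reviewed if available (C.9), and disclosed abuse is reported (C.10). Participation is identifiable and, at best, confidential with limits.

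4. **What enrolees know before the baseline survey.** Under C.1 the remote sequence is identity check, then e-consent link, baseline survey and app login. Under C.8.2 the enrolment form explains confidentiality. By the first trial survey a remote enrolee has shown ID to staff and should have received a second consent. That substantially narrows the exposure for trial data. It does nothing for answers already given in the screener, or for those screened out, who never reach the second form.

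5. **Remote follow-up link.** The C.3 sentence may be true of the survey form taken alone. Read beside C.13, which updates locator details at each follow-up visit, it can be taken as a further promise of anonymity.

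6. **Who is affected.** Eligible ages are 13, 14, 15, 16, 17 and 18, which is six. Ages that give assent are 13 to 17, which is five, so 5 of 6. The 18-year-olds receive the same statements. The enrolment target of 900 does not measure the exposure, because the statements reach people at screening and neither the number screened nor the online share is given.

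**The case against.** The strongest case on the other side is one of sequence. The word appears in a one-line protocol summary of a landing page that leads to a brief screener. Enrolment is a separate step, with an ID check and a second form on confidentiality. Record review starts at enrolment, and abuse reporting and locator updates are described for participants at visits, so all three follow that second form. The script never uses the word *anonymous*; it also promises privacy, is described as a guide, and has lost some text in extraction. The consent forms were removed from the documents, so what youth actually read is unknown.

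Most of this stands, and it limits the point. A reader might infer that enrolled minors answer the trial's sexual-behaviour surveys still believing themselves anonymous, or that the outcome data are biased as a result. The documents do not support either inference, given the ID check and the later form. A reader might also infer that the consent forms omit record review and abuse reporting. That cannot be known from here.

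Two parts do not stand. Restricting the word to the screener does not make it accurate, because B.2.8 and the limited destruction rule in C.8.1 indicate that screening answers are traceable. And a correct later form does not repair an inaccurate statement made before sensitive questions. It is also unclear which consent governs online enrolees: C.8 argues that the click can replace written consent, while C.8.2 requires written consent or assent at the enrolment visit.

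**Conclusion.** The contradiction is real, and it is one of wording. The plan describes as anonymous a process in which screening answers can, on a plain reading of B.2.8, be connected to contactable people, and in which enrolled participants are identified. The practical exposure is mainly at screening, for ages 13-17 and for 18-year-olds, and it persists for anyone screened out. For enrolled participants it is largely mitigated by the ID check and the later consent or assent.

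Harm is a plausible risk and not a demonstrated outcome, and no numerical bias can be derived. The conclusion assumes that the C.8 summary reflects what the page says and that the focus-group approach uses details held from screening. It should be corrected because it concerns what minors are told before sensitive questions. It does not bear on the validity of the statistical analysis.

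**What to change.** - In C.8, replace *anonymous* with *confidential*, and make the same change on the landing page if the word appears there.
- In the C.8.1 script, correct the matching sentence so that it says answers are kept confidential and contact details may be held.
- Before the first screener question, state that contact details may be kept, including for youth found ineligible who may be approached about other parts of the study. State also that confidentiality has limits for those who enrol: the ID check, medical-record review if available, and abuse reporting.
- In C.3, reconcile the sentence on the follow-up link with C.13, for example by saying that the survey form itself asks for no identifiers while the study holds contact details separately, if that is the arrangement.
- Say which consent step governs online enrolees, so that C.8 and C.8.2 agree.

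The cost is a wording change and an IRB submission. No change to design, sample size or analysis is needed.

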The learning activities in each session will be adapted to mobile format, using automated responses, drop-down menus, videos and games to engage the participant in the learning activities. Consistent with the original curriculum, the mobile Much like the current group- based in-person version of MyPEEPS, these characters will present scenarios to open each session and end with a “cliff hanger” to engage participants and motivate participation in the next session. The team at LGS has worked with members of our investigative team, (Drs. [name], [name], [name]) to develop the vision for the technical components of this intervention (see Appendix A for examples of mobile adaptation approaches for activities in each module and sample screenshots). A team of software engineers and project managers at LGS will perform the software development that will be required for this study. LGS is uniquely qualified to build the technical components of the system. We anticipate that MyPEEPS Mobile will be novel, innovative, scientifically sound, scalable, translatable, and highly acceptable; thus, it is likely to have a strong public health impact.

A.3. Participant inclusion and exclusion criteria for all Aims.

To participate in any aspect of the study, participants must be: between 13 and 18 years of age; self-identify as male, non-binary, and/or genderqueer; male sex assigned at birth; understand and read English; live in the US and its territories; own or have access to a mobile device (e.g. smartphone or tablet); self-reported attraction to males and/or a history of sexual activity or interest to engage in sexual activity with other males in the next 12 months; and self-report HIV-negative or unknown status.

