Social and Sexual Networking Web sites and apps: We will recruit participants online through various websites and apps including but not limited to Instagram and Snapchat which are frequented by youth. We will now include ads that will target the entire US and not limited to our 4 local study sites. We will target and recruit study participants through Facebook, which allows targeting of individuals down to age 13. For Facebook, we will use psychographic targeting (in-depth, publicly available consumer data such as interests, city) to advertise only to potentially eligible individuals across the US.

Blogs and YouTube: We will approach bloggers to advertise for the study on sites like: ShadeRoom.com or LoveBScott, and will buy ad space on YouTube for the channels with 'famous YouTubers' that resonate with our target populations.

Media Sites: The study will set up an Instagram profile to promote the study and we will also advertise through outlets like Tumbler, Periscope, and Snapchat.

CBOs/ASOs NYC Email Blast: PHS's Contracting and Management Services division has served as the "Master Contractor" for NYC Department of Health and Mental Hygiene (DOHMH)-funded Ryan White Part A programs. On behalf of the NYC DOHMH, PHS currently administers \$105 million, representing >150 CBOs and ASOs, hospitals, clinics, and mental health clinics. In past studies, PHS has contacted the NYC CBOs and ASOs (via a confidential email list) that receive Ryan White HIV prevention and treatment funding to freely advertise for NYC studies using study-approved flyers and brochures, and proposes to do so for this study.

Dedicated Study Website: This site will present basic content about the study and contain a secure link (via REDCap) for participants to indicate their interest in participation. Participants who leave

their contact information via the website will be contacted by study staff to be screened for eligibility. Eligibility screening will only be done over the phone, online, or in person, **not** via email or text message.

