C.12. COVID-19 Measures.

The investigative team decided to temporarily attach a COVID-19 related block of questions to the MyPEEPS RCT 3-, 6-, 9-, and 12-month follow-up surveys to assess the impacts of the outbreak. The question block will be temporarily attached at the end of all the follow up surveys for the next 3 months, i.e, through the end of August. That should result in getting everyone who

hasn't completed the study at their next visit. If COVID impacts continue through fall of 2020, the investigative team will reassess the need to continue the deployment of this survey block beyond the initial timeframe (end of August). The purpose of this assessment is to better understand the impact of COVID-19 on the current RCT study outcomes specifically as it relates to sexual risk behaviors, PrEP use and HIV/STI testing. The block will include 27 questions concerning: MROS3; Shelter in Place/Stay at Home Orders and Voluntary Self-Quarantine; HIV/Testing During COVID-19 Outbreak; PrEP Use and Refill Access During COVID-19 Outbreak; Risk Behaviors During COVID-19 Outbreak.

C.13. Sound Retention Efforts.

Participants will be asked at the end of the screening what would be the best way for us to remind them of the appointment (voice phone, text, e-mail). We will explain to participants that in all cases a clear boundary exists between the research project and agency staff that prevents the sharing of information we learn about them during the research study with anyone at the agency. Participant retention during the intervention will be enhanced in several ways. First, participants will be compensated \$25 for their time to complete the baseline assessment, up to \$100 for completing all of the MyPEEPS modules, and additional compensation for completing each of the follow-up assessments. Participants will be compensated \$30 for completing the 3 month survey, \$35 for completing the 6 month participants will be compensated \$45 for completion of the 12 month survey. In addition, at each followup visit (3, 6, 9 and 12 months), participants will be asked to update their locator information.

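### The guide script for the screening call names the caller's organisation and the study before checking who has answered, so at some sites the call can reveal a youth's likely sexual orientation to someone else

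*Combined protocol and SAP*

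**What the plan says.** Section C.8.1 (Eligibility screening) lets youths contact the project themselves or, "if contact information is gathered at the recruitment venue, be called, texted or emailed by project staff". Section C.7.a (Recruitment Venues) adds a second source of outgoing contact: people who leave "their contact information via the website will be contacted by study staff to be screened for eligibility", with the telephone among the permitted ways to screen. Section A.3 sets eligibility at "between 13 and 18 years of age" and selects on attraction to, or sexual activity or interest with, males.

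C.8.1 then supplies wording for the caller: "Hi. I work with [e.g. Callen-Lorde Community Health Center] on a research study called MyPEEPS Mobile. Have I reached <insert name>". It introduces this wording as follows: "The following verbal script is a guide to describe the screening process and privacy issues, as outlined in Appendix C".

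The same section covers parents in two ways. If a parent is present at recruitment or enrolment, "such activities would only take place in a private location away from their parents". It also argues that a parent who comes with a child to a centre like the one in the script probably knows already, because such centres are "healthcare and related services providers targeted to lesbian, gay, bisexual, and transgender communities".

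Section C.13 (Sound Retention Efforts) describes a discreet form of contact, but for confirming or rescheduling follow-up visits.

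**The concern.** A caller does not know who has picked up until the identity question is answered. In this script, two identifying facts have been spoken by then, and the youth's own name follows at once. A parent, sibling or other person who hears an LGBT health centre, a research study and then the youth's name can draw the obvious inference.

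The plan treats this kind of exposure as serious elsewhere. Section C.10 regards a waiver of parental consent as essential to the research, and section B.2.5 gives pilot participants an individual login and password so that parents cannot open the app. An unwanted disclosure to a family cannot be undone. It could also lose the youth before enrolment, most plausibly one who is not out at home. The issue is participant safety and recruitment; the estimand and the analysis are not affected.

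**Working it through.** No arithmetic applies, and the plan states no figure to reproduce. The check is to read the script in order, ask when the call is made and what the name reveals, and test each safeguard against the call.

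1. **Order of the opening.** (a) Organisation, (b) study name, (c) question whether the named person has been reached. The script text is damaged by extraction further on, but only after (c). Anything lost there comes too late to protect (a) and (b).

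2. **Is it an outgoing call to someone not yet identified?** Yes. The wording of (c) only makes sense if staff placed the call. C.8.1 (details gathered at venues) and C.7.a (details left on the website) both provide for staff to make contact.

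3. **What does the name reveal?** This depends on the site, because the organisation is a bracketed example. By the protocol's own description, the example centre serves LGBT communities. Among the partners listed in A.1.2, Gay City in Seattle would also be revealing. A children's hospital, which is among the main recruitment sites in both Chicago and Seattle, need not be. The study name does not state orientation by itself.

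4. **Does a safeguard in the documents reach this call?**
   - *Private-location rule (C.8.1).* It is conditional on a parent being present, so staff must know that before they act. On a call they do not know it before they speak.
   - *Parents probably already know (C.8.1).* This concerns a parent accompanying a child to an LGBT-focused clinic. It says nothing about a parent who answers a telephone.
   - *Discreet contact (C.13).* This concerns reminders before follow-up visits, which come after screening and enrolment.
   - *Voicemail or another person answering.* The supplied text has no rule for the screening call.

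5. **Frequency.** Expected disclosures = number of outgoing calls × share using a revealing name × share heard by someone else × share of those listeners who draw the inference. The documents give none of the four factors, so no estimate is offered.

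The sequence is confirmed, and nothing in the supplied text places an identity or privacy check ahead of the two names.

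**The case against.** The strongest case on the other side is that the risk is conditional and the controlling document has not been seen. The script is called a guide and points to Appendix C. C.8.2 also refers to a separate section on the protection of human subjects. Either could hold rules on voicemail or on other people answering. That stands, and it is why confidence is medium. It does not remove the point, because C.8.1 offers this wording as the guide to privacy issues, and its order is clear.

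Several facts also reduce the number of exposed calls. Venue contacts will normally have met staff already, and website contacts left their own details, so these are seldom cold calls. Under C.8 and C.8.1, others screen themselves online or as walk-ins. Eligibility requires owning or having access to a mobile device, which makes a personal number plausible, though not certain. All of this lowers the frequency without closing the gap.

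Three stronger readings are tempting, and the documents do not support them:
- *That the script breaches the plan's own privacy rule.* The rule applies when a parent is present. A call answered by someone else falls outside it, so this is a gap in coverage and not a breach.
- *That C.13 shows staff call without knowing whether the telephone is shared.* The sentence is "Participants will be asked at the end of the screening what would be the best way for us to remind them of the appointment". It concerns appointment reminders. It does not say when contact details or a safe route are first collected, and the venue contact form is not among the documents.
- *That every call names an LGBT centre, or that every misdirected call is a disclosure to a parent.* The organisation is a placeholder, some sites' names reveal little, and the person answering need not be a parent.

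**Conclusion.** The point holds in a limited form. As written in C.8.1, the guide script gives the organisation and the study name before the identity check. Where the inserted name is revealing and someone other than the youth answers, the call can disclose the youth's likely sexual orientation. No safeguard in the supplied text covers that moment.

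The conclusion rests on two conditions that vary by site and by call: the name used and who picks up. It also assumes that Appendix C does not already put the identity check first. A reader might want to attach a number of affected youths, but any such figure would consist wholly of assumptions. The case for change rests on the seriousness and irreversibility of a single disclosure, set against a trivial cost. Confidence is medium.

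**What to change.** Reorder the script in C.8.1, and align Appendix C if it does not already do this:

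1. Ask for the youth by name, giving neither the organisation nor the study.
2. Confirm that the right person is on the line and can talk privately.
3. Only then name the organisation and the study and continue with the existing text.
4. If someone else answers, or the call goes to voicemail, leave neither name.

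If Appendix C already contains these steps, it is enough to correct C.8.1 to match. The cost is a minor script amendment and a short staff briefing. Sample size, data collection and analysis are unaffected.
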